### **MEASURES (see Table 4 for administration schedule).**

**Depression Screening.** Individuals interested in participating in the study will complete an initial phone screening that will include the PHQ-2. The PHQ-2 is a two-question measure that screens for depression. If an individual receives a score of 2 or higher on the PHQ-2 they will be asked to schedule a baseline interview to further determine eligibility.

**Screening for Cognitive Impairment.** Individuals interested in participating in the study will complete an initial phone screening that will include the 6-item Mini Mental Status Exam. The 6-item Mini Mental Status Exam screens for cognitive impairment and dementia. If an individual gets a score of 4 or higher on the Mini Mental Health Status Exam they will be asked to schedule a baseline interview to further determine eligibility.

**Diagnostic interviews.** Diagnostic interviews assessing DSM-V disorders at baseline, post interview and 3-month follow up interviews will be conducted using the Mini International Neuropsychiatric Interview v.7 (MINI; Sheehan et al., 2015). The MINI will be administered by Research Associates blinded to treatment conditions. The MINI is a widely used structured interview with excellent test-retest and interrater reliability. All Research Associates who conduct diagnostic interviews are trained to a standard (see Diagnostic interviewer training & inter-rater reliability, on page 7).

**Measures of subjects' depressive symptoms.** The primary outcome measure for assessing ROST's preliminary effect on depression is the PHQ-9. The PHQ-9 is a nine item measure that assesses depression severity as a continuous measure. Further, the PHQ is a widely-used instrument found to adequately measure depression outcomes in response to depression treatment. Depressive symptoms will also be assessed via the Beck Depression Inventory (BDI). The BDI is a widely-used 21-item scale that assesses depression severity.

**Measures of client functioning.** Overall disability will be measured using Sheehan Disability Scale (SDS; Sheehan, 1996). The SDS is a commonly used three-item measure of functional impairment. In addition, we will measure quality of life using the Quality of Life and Enjoyment Questionnaire (Q-LES-SF). This is a 14-item scale that will be administered at each time point.

**Measures of other symptoms in subjects.** We plan to assess comorbid anxiety symptoms using Generalized Anxiety Disorder Scale, GAD-7. The GAD-7 is a widely used measure with well-established reliability and validity.

**Measure of group cohesion.** We will administer the Group Cohesiveness Scale (GCS; ref), a 7-item self-report questionnaire assessing perceptions of group cohesiveness, during Sessions 1, 4, and 8. The scale has satisfactory psychometric properties (ref).

**Demographics.** Collected demographic information will include gender, date of birth, race/ethnicity, education level, family composition, employment status, and other relevant clinical and demographic characteristics.

**Measures of treatment credibility and beliefs.** Treatment expectations will be measured using the Expectancy Rating Scale (Borkovec & Nau, 1972). This is a four item self-report instrument designed to assess patient expectations regarding change with treatment. The Expectancy Rating Scale will be administered during the baseline interview and again during Session 3 of the ROST intervention so that participants can report expectations after they have been well socialized to the treatment. The Expectancy Rating Scale has high internal consistency and high test-retest reliability (Devilly et al., 2000). Treatment satisfaction will be rated using the Treatment Impressions Rating Scale, a Likert-based self-report instrument.

**Perceived stigma of mental illness.** Participants' perceptions on mental illness stigma will be measured using Perceived Devaluation and Discrimination Scale (PDDS; public stigma). This is a 12-item scale that participants will complete at each time point. We will also be using the Internalized Stigma of Mental Illness Scale which will measure internal stigma. This is a 29-item scale that participants will complete at each time point.

**Measures of Thoughts.** Participants' thoughts will be measured using the Automatic Thoughts Questionnaire and the Dysfunctional Attitudes Scale – Short Form. The 30-item Automatic Thoughts Questionnaire (ATQ) will be completed by participants at every ROST session and has adequate validity and reliability. The 18-item Dysfunctional Attitudes Scale – Short Form will be completed by participants at the baseline, post-treatment, and 3-month follow up assessments. The Dysfunctional Attitudes Scale – Short Form has adequate psychometric properties.

**Measures of Behaviors.** Participants' behaviors will be measured via the Behavioral Activation for Depression Scale (BADS) and the Environmental Reward Observation Scale (EROS). BADS is a 25-item measure that will be completed by participants at every ROST session. The EROS is a 10-item measure that will be completed by participants at all three assessment timepoints.

**Measure of Social Support.** Social support will be measured using the Interpersonal Support Evaluation List - 12 (ISEL-12). This 12-item measure will be completed by participants at baseline, post-treatment, and 3-month follow-up. The ISEL-12 has adequate psychometric properties.

**Measure of Willingness to Accept Help.** Participants' willingness to accept help will be assessed using the 10-item Attitudes Toward Seeking Professional Psychological Help Scale – Short Form and the 24-item Perceived Barriers to Psychological Treatment. Both measures will be completed at baseline, post-treatment, and 3-month follow-up time points.

**Measure of Religiosity.** The 5-item Duke University Religion Index will be used to assess religiosity at baseline.

**Measure of User Engagement.** The 12-item User Engagement Scale-Short Form will be used to assess users' level of engagement with the computer-assisted Raising Our Spirits Together intervention at the post-treatment assessment.

**Measure of Service Use.** Participants' use of mental health treatment and services will be assessed at the 3-month follow up assessment. Treatment and service use will be assessed using the Follow-up Mental Health Service/Medication Use Questionnaire.

**Table 4. Measure Administration Schedule**

Table 4. Measure Administration Schedule				
Category	Measures	Items	Timepoint(s)	Type
Screening	Patient Health Questionnaire-2 (PHQ-2)	2	Screening	PR

	6-item Mini Mental Status Exam	6	Screening	IA
Diagnosis & Symptom Scales	Patient Health Questionnaire-9  (PHQ-9)	10	BL PT FU; Sessions 1-10	PR
	MINI International Neuropsychiatric Interview v. 7 for DSM-V disorders  (MINI)	60 +	BL, PT, FU	DI
Symptom Scales	Beck Depression Inventory  (BDI)	21	BL, PT, FU	PR
	Generalized Anxiety D-7  (GAD-7)	7	BL, PT, FU	PR
Functional Impairment	Sheehan Disability Scale  (SDS)	3	BL, PT, FU	PR
	Quality of Life Enjoyment & Satisfaction Questionnaire – SF  (Q-LES-SF)	14	BL, PT, FU	PR
Mechanisms of Change	Thoughts			
	Automatic Thoughts Questionnaire  (ATQ)	30	Sessions 1-10	PR
	Dysfunctional Attitudes Scale – Short Forms  (DAS)	18	BL; PT; FU	PR
	Behaviors			
	Behavioral Activation for Depression Scale  (BADS)	25	Sessions 1-10	PR
	Environmental Reward Observation Scale  (EROS)	10	BL; PT; FU	PR
	Stigma			
	Perceived Devaluation and Discrimination Scale  (PDDS; public stigma)	12	BL, PT, FU	PR
	Internalized Stigma of Mental Illness Scale  (ISMIS; internal stigma)	29	BL, PT, FU	PR
	Social Support			
	Interpersonal Support Evaluation List -12 (ISEL-12) 	12	BL, PT, FU	PR
	Willingness to Accept Help			
	Attitudes Toward Seeking Professional Psychological Help Scale - SF 	10	BL, PT, FU	PR
	Perceived Barriers to Psychological Treatment 	24	BL, PT, FU	PR
Moderators	Religiosity			
	The Duke University Religion Index 	5	BL	PR
	Depression Severity			
	Beck Depression Inventory  (BDI)	21	BL	PR
	User Engagement			
	User Engagement Scale -Short Form	12	PT	PR
Service Use	Follow-up Mental Health Service/Medication Use Questionnaire 		FU	PR
Treatment Fidelity & Adherence	Collaborative Study Psychotherapy Rating Scale – Cognitive Therapy 	28	Sessions 1-10	IA
	Cognitive Therapy Scale 	13	Sessions 1-10	IA
	Expectancy Rating 	6	BL, Session 3	PR
	Group Cohesiveness Scale 	7	Sessions 1,5,10	PR

Abbreviations: PR: Participant Report; DI: Diagnostic Interview; IA: Independent Assessor

**Diagnostic interviewer training & inter-rater reliability.** Diagnostic interviewers with clinical experience and graduate-level mental health training will be trained to complete interviews (MINI v. 7). They will be trained by [name] and [name] via a didactic training course. Trainees will be asked to rate gold standard interviews until they are able to achieve agreement on diagnostic ratings for three consecutive interviews.

Then, each clinical interviewer will be asked to conduct a role play of two diagnostic interviews. The clinical interviewer will be observed doing three or more interviews until there is a 90% agreement on the MINI. Audio tapes of diagnostic interviews will be reviewed by [name] and [name] and weekly supervisions will be held with clinical interviewers to review tapes, review diagnosis, and address additional training needs.

**Data Analyses.** Primary outcome measures for assessing ROST's preliminary effect on depression relative to ECC are the PHQ-9 and BDI. We expect to enroll 128 subjects, 84 of whom we anticipate will participate in the study after randomization to condition. A sample of 84 subjects who participate in their study condition after randomization should provide power of .8 to find a significant (at 2-tailed  $p < .05$ ) comparative effect size for intervention change of  $d=.8$  or above, which is in ranges found in CBT meta-analyses. Analyses will adjust for BL scores to increase precision and maximize power. Other BL covariates will be examined for association with outcome variables. Those accounting for change in the estimated treatment effect will be retained in final analyses to optimize power and precision. As ROST is group-based, with participants blocked on time of screening prior to randomization, individuals' observations cannot be assumed independent. Due to lack of independence, mixed linear (multilevel) growth modeling will be used to test for the preliminary effect of ROST relative to ECC on outcome variables. Mechanisms of change will be explored by adding change on variables targeted by the intervention (thoughts; stigma) as time-varying covariates to multilevel models predicting change in depression over time. To explore the possibility that treatment effects may differ for those presenting with low v high religiosity and moderate v severe depression, baseline religiosity and baseline depression severity will be examined as potential moderators. Although this RCT is not powered for mediation or moderation tests, effect sizes from these analyses will inform future fully powered research to test mechanisms of change. Analyses will be "intent-to-treat," as all subjects undergoing randomization will be included, and will use multiple imputation methods and pattern mixture modeling to handle data missing at follow-up and sensitivity analyses to examine the influence of missingness on findings.

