### **Aim 1: Develop and test a computer-assisted group-based cognitive behavioral therapy (CBT) for depression (Raising Our Spirits Together (ROST))**

### **Part 3: Randomized Controlled Trial (Phase I/II RCT) of ROST compared to and Enhanced Control Condition**

**Purpose.** The purpose of this project is to conduct a Phase I/II RCT of ROST, evaluating its preliminary effect on depression relative to an enhanced control condition (ECC; see below).

**Intervention Arm: Raising Our Spirits Together (ROST).** ROST is an 8-session, computer-assisted, group-based cognitive behavioral therapy (CBT) for depression that is intentionally designed for delivery by clergy in rural church settings or remotely via secure videoconference software available via the University of Michigan. ROST uses a combination of video-based educational content, text-based educational content, and a character-driven storyline to introduce core CBT concepts, including psychoeducation, behavioral activation, cognitive restructuring, and problem solving. The ROST intervention package also includes a participant workbook and intervention manual for group leaders.

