**Randomization.** Persons meeting eligibility criteria will be randomized to ROST or the ECC. Randomization will occur in replicated blocks across conditions. This procedure will repeat until 7, six-member ROST groups and 7, six-member ECC groups are assembled. If participant flow prevents timely assembly, smaller groups will be considered to avoid extended delays.

**STUDY SITES:** There will be two study sites for the RCT, located in Hillsdale County. The study sites are our partner churches, Trinity Lutheran Church and Jonesville First Presbyterian Church. ROST will either be delivered in-person at one of our partner churches, or virtually, via secure, web-based videoconferencing software available through the University of Michigan. The pastors will facilitate in-person and virtual ROST groups.

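### The Measures section makes the PHQ-9 the sole primary outcome, but Data Analyses makes the PHQ-9 and BDI both primary without a rule for deciding between them

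*Combined protocol and SAP*

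**What the plan says.** Two passages of the combined protocol and SAP define the primary outcome for the same purpose, the effect of ROST on depression.

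- **Measures, paragraph on depressive symptoms.** In the singular, the primary measure for ROST's "preliminary effect on depression is the PHQ-9". The BDI follows as an addition: "Depressive symptoms will also be assessed via the Beck Depression Inventory (BDI").
- **Data Analyses (the paragraph after Table 4 and the interviewer-training text).** In the plural, the primary measures for ROST's "preliminary effect on depression relative to ECC are the PHQ-9 and BDI".

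The only significance level, two-tailed p < .05, stands in the power sentence of Data Analyses. It is attached there to a single "comparative effect size for intervention change" of d = .8 and is not given as a threshold for each scale. The multilevel model "will be used to test for the preliminary effect of ROST relative to ECC on outcome variables", with no order among those variables.

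Other sections do not settle the matter. The Purpose statement for Part 3 speaks of "evaluating its preliminary effect on depression relative to an enhanced control condition" and names no scale. Table 4 schedules both scales at baseline, post-treatment and follow-up without marking either as primary, though a visit schedule would not be expected to.

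**The concern.** The Measures section does rank the scales: PHQ-9 first, BDI as a supplement. Data Analyses, the section an analyst would follow, puts them level and says nothing about how two results become one conclusion. Both statements are current text, and they cannot both stand.

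The effect on depression is the first stated aim of the RCT and the only test for which the plan offers a power statement. If one scale reaches significance and the other does not, the reader cannot tell from the plan whether the primary result was met. A choice made after the results are seen could not be defended as prespecified, whichever way it went.

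**Working it through.** **1. The two rules side by side**

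| Result | Under Measures | Under Data Analyses |
|---|---|---|
| Both significant | met | met |
| PHQ-9 only | met | no rule |
| BDI only | not met | no rule |
| Neither | not met | not met |

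The two middle rows are the problem.

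**2. The plan's own figure.** Data Analyses gives power of .8 for d = .8 with 84 participants (42 per arm under Enrollment and Participants). A plain two-sample t test gives noncentrality .8 × √(42/2) = 3.67 on 82 df and power of about .95 at two-sided .05, so .8 is not reproduced from the stated inputs. That is a separate question, and nothing below depends on how it is answered.

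**3. How often the scales would split.** Inputs: the plan's stated power of .8 for each scale, equal effects on both, and a bivariate normal distribution for the two test statistics with correlation ρ. The documents give no ρ, so .7 to .9 is an assumption.

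P(exactly one significant) = 2 × [.80 − P(both)]

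- ρ = .7: 2 × (.800 − .713) = .174
- ρ = .9: 2 × (.800 − .750) = .100

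On these assumptions, 10% to 17% of trials would land in the two rows without an agreed answer.

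**4. Error rate if either scale were enough.** This takes each scale at two-sided .05 with no true effect on either.

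- Either scale, any direction: 1 − P(|Z1| ≤ 1.96 and |Z2| ≤ 1.96)
- Either scale, favouring ROST: 1 − P(Z1 ≤ 1.96 and Z2 ≤ 1.96)
- Both scales: .05 + .05 − P(either)
- Each at .025: the first formula with the two-sided .025 critical value

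| ρ (assumed) | Either, two-sided | Either, favouring ROST | Both required | Each at .025 |
|---|---|---|---|---|
| .5 | 9.1% | 4.5% | 0.9% | 4.6% |
| .7 | 8.3% | 4.2% | 1.7% | 4.3% |
| .8 | 7.8% | 3.9% | 2.2% | 4.0% |
| .9 | 7.0% | 3.5% | 3.0% | 3.6% |

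For one scale the corresponding rates are 5% two-sided and 2.5% favouring ROST. The excess at ρ from .9 to .7 is therefore 2.0 to 3.3 points two-sided, or 1.0 to 1.7 points in favour of ROST. At ρ = 0 the two-sided rate is 1 − .95² = 9.75%, the upper limit. The both-required column assumes no effect on either scale. If one scale truly responds and the other does not, that rule's error can rise to 5% but not beyond.

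**The case against.** The strongest case on the other side is that this is a pilot testing a preliminary effect, that the repair is a matter of wording, and that the numerical harm needs an either-scale rule that appears nowhere in the plan. Under the other two readings (PHQ-9 alone, or both required) the 5% level holds.

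Most of that stands, and it limits the claim. A reader might infer that the trial runs at a 7% to 8% false-positive rate. The documents do not support this: they state no success rule, and p < .05 appears only in the power sentence. The two-sided figure also counts errors against ROST; the excess in false findings for ROST is about half as large. The correlation range is assumed. What matters is the correlation between two baseline-adjusted treatment estimates, and a value below .7 cannot be excluded from the documents.

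A reader might also say that the two sections give opposite answers when the scales disagree. That too goes beyond the text: Measures gives an answer and Data Analyses gives none.

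The objection does not remove the contradiction. Pilot status lowers the consequence, but the plan still proposes a significance test with a power statement for this comparison. It describes only the mediation and moderation analyses as unpowered.

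**Conclusion.** The concern holds as a direct contradiction about which outcome is primary. It should be corrected before outcomes are compared by arm. This conclusion rests on the text alone and on no assumed correlation.

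The size is conditional. If either scale at .05 were accepted as success, the two-sided error would be about 7.0% to 8.3% (ρ from .9 to .7; 9.1% at .5), and the rate of a false finding for ROST about 3.5% to 4.2% against 2.5%. Under either alternative reading there is no inflation above 5%. The figures show what an unstated rule would cost; they do not describe an error rate the plan has adopted.

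**What to change.** Reconcile Measures and Data Analyses before outcomes are compared by arm. The choice is the sponsor's.

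- **Simplest: amend Data Analyses to match Measures.** Name the PHQ-9 as sole primary outcome, tested at two-sided .05, with the BDI secondary or tested in fixed sequence after it. The BDI alone could then no longer carry a primary claim.
- **Alternative: keep both scales primary.** Say so in both sections and state the rule: either each scale at .025, or both required at .05. The cost is some power. With 42 per arm and d = .8, before any allowance for clustering or baseline adjustment, per-scale power falls from about .95 at .05 to about .91 at .025. Requiring both at .05 gives about .93 to .94 at assumed correlations of .7 to .9 (normal approximation).

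Whichever is chosen, state the significance level as a decision threshold and not only inside the power sentence. No new data or participants are needed.

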All recruitment materials for the open pilot will avoid stigmatizing terms and include diverse images in terms of race/ethnicity, gender, and age, promoting inclusiveness.

**Inclusion.** In order to participate in this study, persons must: 1) currently live in Hillsdale, Branch, Jackson, Calhoun, or Lenawee County, Michigan. All persons residing in these counties may participate, regardless of religious beliefs; however, like Alcoholics Anonymous, participants will be informed of and must accept that non-denominational Christian-based quotes and images are included; 2) screen positive for at least mild depressive symptoms on the Patient Health Questionnaire-9 (PHQ-9 $\geq$ 5); and 3) not currently receive Cognitive Behavioral Therapy (CBT) treatment. Persons taking medication for depression may participate. Medication use will be monitored. Participants will be advised to continue taking any psychiatric medication according to their clinician/physician's instructions; though medication stabilization will not be required for inclusion. [name] research in non-mental health settings suggest medication stabilization is not feasible given the likelihood of multiple prescribing providers. Depressive disorder diagnoses will be assessed via structured interview (MINI v 7), but is not required for inclusion. Depressive disorder diagnosis will be considered in analyses. This increases access for underserved persons with a range of symptoms; helps fill groups faster; and is most generalizable to real world implementation.

**Exclusion.** Persons will not be eligible for the study if they 1) are non-English speaking; 2) currently receive regular CBT for depression (>1 time per month); 3) ever completed a course of CBT ( $\geq$ 8 sessions); 4) have a psychotic disorder; 5) currently use opiates cocaine; 6) have cognitive impairment ( $\geq$ 2 incorrect items on the 6-item mini mental status exam); or 7) have prominent suicidal/homicidal ideation with imminent risk. Indicators for imminent risk will be assessed by the interviewer. Subjects with significant suicide/self-harm or homicide risk must be excluded on ethical grounds and will receive appropriate resources and referrals (see Protection of Human Participants).

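### Baseline covariates are retained because they move the treatment estimate, a criterion that does not serve the stated aim of power and precision (optional, low severity)

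*Combined protocol and SAP*

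**What the plan says.** All the relevant analysis text is in the Data Analyses paragraph that follows Table 4.

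- One adjustment is fixed: "Analyses will adjust for BL scores to increase precision and maximize power".
- A screen follows: "Other BL covariates will be examined for association with outcome variables". No candidate list, test or cut-off is given.
- Then comes the retention rule: "Those accounting for change in the estimated treatment effect will be retained in final analyses to optimize power and precision". The size of change that counts is not stated. The sentence cites a reference.
- The model is multilevel, chosen because of grouping: "Due to lack of independence, mixed linear (multilevel) growth modeling". The paragraph does not say whether baseline enters as a covariate or as the first wave.
- The analysis is by intention to treat, "as all subjects undergoing randomization will be included".

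The pool of possible candidates is wide. Table 4 marks 14 participant-level instruments at baseline other than the PHQ-9. The Demographics paragraph adds six items: "Collected demographic information will include gender, date of birth, race/ethnicity, education level, family composition, employment status". Separately, the Inclusion paragraph says "Depressive disorder diagnosis will be considered in analyses", without saying in which analysis or how.

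**The concern.** The criterion and the aim do not match. Under randomization a covariate shifts the treatment estimate by roughly its coefficient times its chance imbalance between arms. It improves precision through its coefficient alone. A strong predictor that happens to be balanced shifts nothing and is dropped, although it would narrow the interval. A weak predictor that happens to be imbalanced may be kept.

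The final model also becomes a function of the treatment estimate it is meant to test, and its standard error takes no account of that selection. The trial's stated purpose is to evaluate a preliminary effect, so the width and honesty of the interval are what a later trial would build on.

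**Working it through.** **The plan's own figure.** The plan gives no figure for the covariate rule. Its one related figure is power .8 at d=.8 with 84 participants. An unclustered two-sample t calculation with 42 per arm, two-sided .05, gives .952. That mismatch is a separate matter and nothing below depends on it.

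**Assumed inputs, not in the documents.** Within-arm SD 1; baseline score R2 .25; three prognostic covariates adding R2 of .02 to .10 in total; independent candidates; retention if the estimate moves by more than 10%; one post-treatment outcome with baseline as covariate; no clustering. From the documents: 42 per arm, and 14 or 20 candidates (Table 4, or Table 4 plus six demographic items).

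**Step 1: what the rule selects on.** At added R2 .10, each prognostic covariate has coefficient √(.10/3) = .183. The SD of the between-arm difference in its mean is √(1/42 + 1/42) = .218. The shift in the estimate therefore has SD .183 × .218 = .040.
- At a true .5 SD the cut-off is .05, and .05/.040 = 1.25, so the chance of retention is about .21. Simulation, in which the coefficient and the effect are estimated, gives .25.
- At d=.8 the cut-off is .08, and .08/.040 = 2.0, a chance of about .05. Simulation gives .10 to .11.

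Most of the useful covariates are dropped, and more so when the treatment works better.

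**Step 2: what a fixed list can gain.** Variance relative to baseline-only is ((.75 − added R2)/.75) × 80/77 for three covariates at N=84. With a baseline-only SE of .190 and a true .5 SD, power is Φ(.5/SE − 1.99):

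| Added R2 | Relative variance | SE | Power |
|---|---|---|---|
| baseline only | 1 | .190 | .74 |
| .10 | .900 | .180 | .78 |
| .05 | .970 | .187 | .75 |
| .02 | 1.011 | .191 | .73 to .74 |
| 0 | 1.039 | .194 | .72 |

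Break-even is at added R2 = .75 × 3/80 = .028.

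**Step 3: the rule without the screen.** Simulation, 20,000 trials per setting, true .5 SD, added R2 .10. Order: baseline only / rule / list of exactly the three prognostic variables.
- 3 candidates: power .74/.77/.79.
- 14 candidates: power .74/.75/.78; sampling SD .190/.191/.180; the rule's mean SE .187.
- 20 candidates: power .74/.74/.78; sampling SD .191/.196/.182; the rule's mean SE .188.
- 14 candidates at d=.8: power .985/.987/.992; mean SE .190/.188/.180, so the rule's interval is .188/.180 = 1.04 times as wide as the list's.
- 14 candidates with the 103 expected at randomization: power .82/.84/.86.

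**Step 4: the rule after an association screen at p<.10.** With 14 candidates and added R2 .10, power is .76 and sampling SD .191, essentially the baseline-only SD. With no true effect and added R2 of .05 to .10, the mean SE was .180 to .185 against true SDs of .186 to .196. The screen does not repair the criterion, and the reported SE is still too small.

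**Step 5: null rejection.** Rule without screen: .055 (14 candidates, added R2 .10), .060 (R2 .05), .061 (20 candidates). With the screen: .053 to .061. Fixed list: .046 to .050. Without the screen, it is .052 with an absolute cut-off of .05 SD and .048 if candidates correlate .3.

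**Step 6: an imperfect list.** 4,000 runs, Monte Carlo SE about .007, 14 candidates, true .5 SD.

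| Added R2 | Baseline only | Screened rule | List: 3 right | 2 right | 1 right |
|---|---|---|---|---|---|
| .10 | .743 | .764 | .779 | .760 | .742 |
| .05 | .750 | .763 | .765 | .749 | .740 |

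**Step 7: the planned kind of model.** These checks used three complete waves and a random intercept.
- Baseline as first wave: adding main-effect covariates leaves the treatment-by-time estimate unchanged (largest difference 5e-15) and the SE at .109. In that special case the rule would keep nothing and a main-effects list would gain nothing.
- Baseline as a covariate, with post-treatment and follow-up as outcomes: the list moves the SE from .155 to .153, about 1%.

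**The case against.** The case for leaving the text alone is substantial.

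- The plan does contain a prognostic step. The retained covariates are most naturally read as those that first showed association with outcome. A reader might infer that prognosis is ignored altogether; the text does not support that. What stands is that the final criterion is still change in the estimate, and Step 4 shows that the screen does not restore precision.
- A reader might infer that a named list would clearly raise power. The documents give no covariate R2, and the gain in Step 3 needs the list to contain exactly the right variables. With two of three right, its power is about that of the screened rule; with one right, it is about that of baseline-only. Part of the screened rule's power does come from an SE that is too small (.186 against a true SD of .191 at added R2 .10).
- A reader might infer a material type I error problem. The excess is at most about one point under independent candidates and nearly vanishes when they correlate. The depression, anxiety, disability and quality-of-life scales in Table 4 plausibly do correlate.
- The rule is not useless everywhere. In a simulation with 10 candidates and a joint partial R2 of .20, it lowered the sampling SD from .191 to .184, against .173 for the list.
- Baseline-score adjustment, probably the main source of precision, is already fixed, and this is a pilot. The rule also cites a reference that could not be consulted here, and the 10% cut-off is an assumption.

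These points reduce the severity. They do not reconcile the criterion with its stated aim.

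**Conclusion.** The point holds as a low-severity, optional correction. The plan states a retention rule whose criterion is not the one that delivers its stated purpose, and the rule makes the primary model depend on the treatment estimate.

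At 84 participants, with 14 independent candidates and added R2 of .05 to .10, the rule's true sampling SD is no better than that of baseline-only adjustment. Its reported SE is slightly too small, and null rejection is up to about one point above that of the fixed alternatives.

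The benefit of change is mainly a prespecified model with an honest SE. Over baseline-only, power might rise by about 1 to 5 points if the named variables add R2 of .05 to .10, or fall by 1 to 2 points if they add nothing. In a repeated-measures model with baseline as covariate, the SE improvement was only about 1%. All of these sizes rest on inputs the documents do not give, and the power figures come from a single-outcome regression without group clustering. Confidence is medium.

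**What to change.** Before any outcome is compared by arm, delete the change-in-estimate criterion and state the primary model:

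- The baseline value of the outcome enters as a covariate, with post-treatment and 3-month follow-up as the outcome waves.
- At most two or three further variables, collected before randomization, are named in advance for expected prognostic value beyond the baseline depression score. They are kept whatever they do to the treatment estimate. If none is credibly prognostic, use the baseline score alone.
- Say whether depressive disorder diagnosis is on that list. If it mostly repeats the baseline score, it will add little.
- If any variables are added, report the baseline-only model as a sensitivity analysis.

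The cost is one or two sentences and no new data. The price is one degree of freedom per covariate, less freedom to add covariates later, and about 1 to 2 power points (.74 to .72 at a true .5 SD) if three listed variables turn out not to be prognostic.
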